1.1. Document History

Version	Date of Issue	Summary of Change
1.0	08/03/2024	Initial version
2.0	18/03/2024	
3.3 Primary objective #1: The 6 score dimensions have been specified.3.3 Secondary objective: Since information regarding tolerance and adherence is available, assessment of this objective will be conducted.3.5 The definition of the MTT24.5 program has been updated.3.7 Power calculation has been incorporated.3.8 f-BMR and BMR procedure has been described.4.2 Outcomes related to adherence have been defined.5.3.4 Statistical method for adherence outcome analysis has been outlined.
3.0	20/03/2024	
5.3.1 and 5.3.2 Standardized effect size calculation has been updated

1.2. List of Abbreviations and Definitions of Terms

ACE	Addenbrooke's Cognitive Examination
BMRI	Brain magnetic resonance imaging study
CRS	Cognitive Reserve Score
IQR	Inter quartile range
MTT24.5	Mental Training Tech 24.5
SCD	Subjective cognitive decline
SD	Standard deviation
TECH	High-impact cognitive stimulation modalities

2. Introduction

The purpose of this document is to describe the planned analysis and reporting for the neuroplasticity applied program “MENTAL TRAINING TECH 24.5”

This statistical analysis plan is based on the latest version of the protocol dated April 17, 2023 revised on January 15, 2024.

3. Protocol summary

3.1 Background

The human brain has the ability to change and adapt throughout life, challenging the previous belief that the process of brain aging was irreversible. This paradigm shift, driven by scientific discoveries such as those of Eric Kandel, highlights the importance of neuroplasticity, the brain's ability to reorganize, in preserving and recovering cognitive functions. Therefore, it is necessary to incorporate brain training programs into culture and medicine to harness this adaptive capacity of the brain and improve quality of life at all stages.

Based on this knowledge situation, the applied neuroplasticity program "Mental Training Tech 24.5" (MTT24.5) has been developed as a method for inducing brain plasticity to enhance, protect, and preserve cognitive abilities, fostering from a physiological model of brain connection growth and strengthening

3.2 Study hypothesis

- *Hypothesis 1*

The MTT24.5 cognitive training program is associated with cognitive brain functional changes, as it may increase performance in memory and/or attention and/or verbal fluency and/or language and/or visuospatial skills in adults without clinical cognitive impairment or with subjective cognitive decline (SCD).

- *Hypothesis 2*

The MTT24.5 cognitive training program is associated with changes in brain neuroplasticity, as it may increase or modify the volume of specific brain areas and/or their level of activation.

- *Hypothesis 3*

The improvement in performance of the cognitive abilities listed in Hypothesis 1 is associated with changes in brain neuroplasticity.

- *Hypothesis 4*

Different baseline conditions may modulate responses to the cognitive program, including: a) baseline cognitive reserve, b) history of dementia, c) non-communicable chronic diseases, d) lifestyle habits, and e) medication use.

3.3 Study objectives

- ***Primary objectives***

1. Evaluate the effects of MTT24.5 on cognitive abilities such as memory, attention, orientation, verbal fluency, language and visuospatial skills
2. Assess the effects of MTT24.5 on brain structural characteristics, considering brain volumes in globally standardized areas, as well as those associated with cognitive abilities.
3. Examine the effects of MTT24.5 on brain activation, defined as patterns of metabolism distribution and neuronal perfusion overall, and according to cognitive brain areas with taxonomic mapping.
4. Determine if there are response phenotypes based on the distribution of individual baseline characteristics, such as age, gender, lifestyle factors, medical history, medications, family history of dementia, diet, and baseline cognitive reserve score.

- ***Secondary objective***

Analyze the tolerance and adherence to MTT24.5, and its association with outcomes regarding cognitive variables, as well as structural and/or functional brain changes.

3.4 Study design

It is a prospective, non-randomized controlled clinical study that evaluates the effectiveness and tolerance of a cognitive intervention.

3.5 Interventions description

- ***Control Group***

Participants in this group will not receive any specific cognitive training program during the study period. They will continue with their usual activities and routines.

- ***Intervention Group:***

Participants in this group will receive the cognitive training program MTT24.5.

The MTT24.5, developed as a binomial DATA/TECH, provides the brain with 35 new knowledge (DATA) classified in formal, natural, social, and cultural areas. The TECH consists of 100 high-impact cognitive stimulation modalities designed to enhance memory, attention, verbal fluency, and visuospatial skills. During the program, the brain receives 35 new pieces of knowledge, and the 100 TECHS created to promote changes in brain functionality, improve synaptic efficiency, and achieve permanent plastic changes. The program's duration is approximately 24.5 hours spread across 12 to 16 weeks including in-person training classes of 1.5 hours each week. The

training is complemented with weekly online activities, which entail an additional average dedication of 4 hours.

3.6 Population

- ***Inclusion criteria***

- Adults aged 21 years and above.
- Ability to understand the instructions for the training tasks.

- ***Exclusion criteria:***

- Planned absence that would hinder participation in the program.
- Hearing, visual, or motor deficits that would impede participation in the program.
- History of severe degenerative neurological diseases as these conditions may significantly impact brain plasticity and cognitive abilities.
- History of severe psychiatric disorders as they may influence brain reorganization and complicate interpretation of the results.
- Unstable treatment or planned changes in medication that may affect brain function and alter results.
- History of current or recent excessive substance use (within the past 6 months) including alcohol or drugs as these substances may influence brain function and neuroplasticity.

3.7 Sample size

The sample size of 76 subjects (56 cases and 20 controls) will provide a power of at least 80% to detect a minimum difference of 4 points in the score improvement between the two groups, assuming a maximum standard deviation of 5.4 points. This minimum difference of 4 points corresponds to a minimum effect size of 0.8.

3.8 Data collection

Information will be collected on study specific forms/procedure.

- ***Cognitive Reserve Score (CRS):*** It consists of a validated cognitive reserve scale used with authorization from Roldan L. et al. The CRS records the frequency of cognitively stimulating activities carried out throughout life. A total of 24 items are distributed across four aspects: activities of daily living, education/information, hobbies, and social life. The CRS will be obtained for each subject at baseline (pre intervention).

- **Medical and Lifestyle History Form.** Self-administered medical and lifestyle history form called STEPS 5, adapted from www.who.int/chp/steps, and previously used in the Latin American OPTIMO study. This form will be administrated for each subject at baseline (pre intervention).
- **The Addenbrooke's Cognitive Examination-III.** Brief cognitive test that evaluates five cognitive abilities: attention, memory, verbal fluency, language, and visuospatial skills. The ACE score will be obtained for each subject at baseline (pre intervention) and post intervention.
- **Functional brain magnetic resonance imaging study (f-BMR) and Brain magnetic resonance (BMR).** The study consisted of the acquisition of two magnetic resonance sequences in a Philips Ingenia 3T resonator as follows:
 - a) High resolution 3D T1w sequence, used for measuring volumes of gray and white matter.
 - b) EPI sequence: used for functional MRI.

For functional magnetic resonance imaging, a block paradigm was used, consisting of 1 minute of rest followed by 1 minute of stimulation. The block was repeated 5 times for a total acquisition time of 10 minutes. During the stimulus, the subjects visualized a screen a word representing a color, but painted in a different color, so the same way as in the “interference” section of the Stroop test; The task was to think, silently, the written word, trying to ignore the color information. The task was explained and briefly practiced with the subjects before beginning the acquisition of images to reduced associated stress reaction.

Prosecution:

The images obtained were exported in DICOM format and converted to NIFTI format through the dcm2niix tool. T1w images were processed with the tool vol2Brain (<https://www.volbrain.net/>), which segments the brain into multiple structures, cortical and subcortical structures automatically, and reports the volumes of each structure. Functional magnetic resonance images were processed with SPM12 software to obtain t-statistic maps of the whole brain, registered to the T1 image. Flirt and fnirt tools were used, included in the FSL software package (<https://fsl.fmrib.ox.ac.uk/fsl/fslwiki>), to register the T1 image to MNI space; the transformation obtained was then applied to the t map to bring it to the MNI space.

Once the t map was obtained in the MNI space, it was superimposed with the AAL atlas (Automated Anatomical Atlas, (Neuroimage, 15 (2002), pp. 273-289), included in MRICron software(<https://www.nitrc.org/projects/mricron>)). For each plot of the atlas, the value was calculated average of the parameter t for those voxels with a value of t greater than 3. To those regions without voxels greater than 3 were assigned a value of 0.

The results were registered as:

a) "Volumes.zip file" which contains a .csv file and a .pdf file for each patient. The .pdf contains a report with the volumes of different structures of the brain, both in absolute terms (cm3) and relative (% of the total), and values reference of normal populations corrected for age and sex. The .csv contains the same values, organized by structure, in tabular format.

b) Activations.csv file: which contains the average value of the thresholded t-statistic for each region of the AAL atlas and for each patient, according to what is explained in the previous section.

In addition, images of all patients are available, both the data raw in DICOM format like NIFTI, as well as t maps.

This study will be conducted on a subset of the subjects at baseline (pre intervention) and post intervention.

3.9 Study outcomes

- ***Primary outcome***
 - Cognitive ability improvement
- ***Secondary outcomes – related to cognitive abilities***
 - Memory ability improvement
 - Attention ability improvement
 - Orientation ability improvement
 - Verbal fluency ability improvement
 - Language ability improvement
 - Visuospatial skills ability improvement
- ***Secondary outcomes – related to brain volume outcomes:***
 - Anterior cingulate gyrus right thickness improvement
 - Anterior cingulate gyrus left thickness improvement
 - Anterior cingulate gyrus right volume improvement
 - Anterior cingulate gyrus left volume improvement
 - Cerebrum grey matter total volume improvement
 - Cortical Grey Matter volume (%) improvement
 - Cortical Grey Matter volume (cm3) improvement

- Middle frontal gyrus right thickness improvement
- Middle frontal gyrus left thickness improvement
- Middle frontal gyrus right volume improvement
- Middle frontal gyrus left volume improvement

- ***Secondary outcomes – related to brain activation:***

- Left anterior cingulate improvement
- Right anterior cingulate improvement
- Left medial cingulate improvement
- Right medial cingulate improvement
- Left posterior cingulate improvement
- Right posterior cingulate improvement

4. Outcomes definitions

4.1 Primary outcome

The primary study outcome, cognitive ability improvement, will be assessed through the difference between the post intervention ACE score and the pre intervention ACE score. This score ranges from 0 to 100.

4.2 Secondary outcomes

- ***Outcomes related to cognitive abilities***

The ACE score comprises six dimensions, each evaluating a different domain: Memory, attention, orientation, verbal fluency, language, and visuospatial skills abilities.

Each ability outcome improvement will be assessed using the respective sub-dimensions of the ACE score and computing the difference between post intervention and pre intervention sub-score:

- Memory ability sub-score improvement
- Attention ability sub-score improvement
- Orientation ability sub-score improvement
- Verbal fluency ability sub-score improvement
- Language ability sub-score improvement
- Visuospatial skills ability sub-score improvement

The memory ability sub-score ranges from 0 to 26, the attention abilities sub-score ranges from 0 to 8, the attention abilities sub-score ranges from 0 to 10, the verbal fluency sub-score ranges from 0 to 14, the language sub-score ranges from 0 to 16, and the visuospatial skills abilities sub-score ranges from 0 to 26.

- ***Outcomes related to brain volume and brain activation:***

Brain Volume and brain activation improvement outcomes are obtained from the Brain magnetic resonance imaging study (BMRI) and computing the difference between post intervention and pre intervention values. These outcomes are measured for a subset of the intervention group at baseline and post-intervention. The selected subset of measure that are considered in this study are listed in point 3.9

- ***Outcomes related to adherence:***

Compliance with the study protocol is assessed via two measures:

- (1) the number of days that participant completed (“on site days”)
- (2) the number of home training complementary exercises that participants completed. As participants were instructed and reminded to complete weekly sessions, the number of active days was used as the primary measure of a participant’s ongoing engagement and compliance with the study protocol.

5. Statistical analyses

5.1 Subject Disposition

A CONSORT flow diagram will be used to summarize the number of subjects who were:

- Enrolled
- Enrolled to each group
- Discontinued in each group
- Included in the Cognitive analysis in each group
- included in the Brain volume and activation analysis

5.2 Distribution of socio demographic and clinical characteristics

All continuous variables will be summarized using the following descriptive statistics: mean, standard deviation (SD) and range if data presented a normal distribution and median, inter quartile range (IQR) and range if data skewed. The frequency and percentages (based on the non-missing sample size) of observed levels will be reported for all categorical measures.

5.3 Statistical analysis methods

5.3.1 Objective 1

The mean baseline ACE score and standard deviation (SD) will be reported for both the intervention and control groups. Additionally, the improvement from baseline to the end of the program will also be presented for each group.

To assess the impact of MTT24.5 on cognitive abilities, a linear model will be utilized for each cognitive domain (global, memory, attention and orientation, verbal fluency, language, and visuospatial skills). Each model will use the improvement score value as the outcome variable and the group (intervention and control) as the independent variable. The group term will evaluate the non-standardized intervention effect, indicating whether the mean improvement in scores (change from baseline) differs between the control and intervention groups. The effect size is defined as the difference between the mean improvement on the intervention group and the mean improvement on the control group.

To compute standardized effect sizes, Cohen's d Statistic will be calculated. Standardized metrics facilitate comparisons across different scores.

The fulfillment of model assumptions will be assessed, and if they are not met, proposals for improvement will be suggested.

5.3.2 Objective 2 and 3

For these objectives the subset of subjects within the intervention group who underwent BMRI will be considered. No control group is available for this assessment.

To evaluate the impact of MTT24.5 on brain volume and brain activation, a t-test will be conducted for each brain improvement outcome to determine whether the mean improvement differs from zero.

For each brain outcome, the non-standardized effect size will be reported as the mean improvement, while the standardized effect size will be calculated using the Cohen's d Statistic for repeated measures.

5.3.3 Objective 4

To identify potential response phenotypes based on individual baseline characteristics (including age, gender, medical history, medications, family history of dementia, and baseline cognitive reserve score), a linear model will be employed for each covariate of interest. The primary outcome will be modelled with the covariate of interest, the group variable, and their interaction. This interaction term will assess whether the intervention effect varies across covariate groups.

To summarize the results, a forest plot displaying the standardized effect size for each covariate group will be generated.

Covariate / Subgroups of interest:

- Sex (female, male)
- Age (<=65 years, >65 years)
- Years of Education (<=12 years, >12 years)
- Cognitive reserve (low, high)
- ACE score at baseline (<85, >85)
- Diabetes history (yes, no)
- Hypertension history (yes, no)
- Dyslipidemia history (yes, no)
- Dementia family history (yes, no)
- Statins /AAS use (yes, no)

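### Non-randomized comparison, but no cognitive model estimates an overall group effect adjusted jointly for baseline factors

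*SAP*

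**What the plan says.** SAP 3.4 (Study design): "It is a prospective, non-randomized controlled clinical study". The primary outcome in 4.1 is the "difference between the post intervention ACE score and the pre intervention ACE score".

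SAP 5.3.1 (Objective 1) fits one linear model to the global score and one to each domain: "Each model will use the improvement score value as the outcome variable and the group (intervention and control) as the independent variable". It continues: "The group term will evaluate the non-standardized intervention effect". The effect is fixed as a crude contrast: "The effect size is defined as the difference between the mean improvement on the intervention group" and the corresponding mean in controls. Table 2 has rows only for this contrast and its standardized form.

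SAP 5.3.3 (Objective 4) is the only place where covariates enter a model. There, "a linear model will be employed for each covariate of interest", and "The primary outcome will be modelled with the covariate of interest, the group variable, and their interaction". The stated aim is to find response phenotypes, and the output is a forest plot of effects by subgroup. Ten covariates are listed. Age, years of education, cognitive reserve and baseline ACE each appear as two categories.

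Table 1 describes the groups at baseline but is not linked to any analysis. The SAP contains no multivariable model, propensity score, matching, weighting or adjusted sensitivity analysis.

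**The concern.** Without randomization, the groups may differ in factors that predict how much the ACE score changes. Taking post minus pre removes stable differences in level. It does not remove differences in factors related to the amount of change, and Hypothesis 4 in SAP 3.2 itself expects baseline conditions to influence response.

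The group coefficient, its 95% CI and its p-value therefore mix the programme effect with any such imbalance. Because the tests are two-sided (5.5), imbalance in either direction raises the false-positive rate above 5%. Imbalance favouring controls also hides a real effect and lowers power below the planned 80%.

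A reader could see an imbalance in Table 1 and single-covariate subgroup effects in the forest plot. There would still be no prespecified adjusted overall estimate to turn to, and any adjustment made later would be chosen with the data in view.

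**Working it through.** **Inputs from the SAP.** 56 intervention and 20 control participants, a 4-point difference and an SD of improvement of 5.4 (3.7); two-sided 5% tests (5.5); the group-only model (5.3.1).

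**Assumed, because the SAP gives no values.** Between-group imbalance d in a covariate, in SD units; correlation r of that covariate with improvement; the shares of variance used in step 5.

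**1. The plan's own figure.** SE = 5.4 × √(1/56 + 1/20) = 1.407. The noncentrality is 4/1.407 = 2.84. A noncentral t with 74 df gives power 80.1% (normal approximation 81.2%). The stated power of at least 80% is reproduced, and it belongs to the group-only comparison.

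**2. One unadjusted covariate.** Bias = d × r × 5.4. Type I error uses noncentrality bias/1.407. Power when the bias runs against the programme uses (4 − bias)/1.407.

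| Case | d | r | Bias (points) | Share of 4 points | Type I error | Power, opposite sign |
|---|---|---|---|---|---|---|
| Low | 0.3 | 0.2 | 0.32 | 8% | 5.6% | 73.2% |
| Middle | 0.5 | 0.3 | 0.81 | 20% | 8.8% | 61.0% |
| High | 0.7 | 0.4 | 1.51 | 38% | 18.6% | 41.5% |

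**3. Why one covariate at a time is not enough.** Take two covariates with mutual correlation 0.3, both imbalanced in the same direction (opposite directions would partly or wholly cancel). The crude bias is 5.4 × d × 2r/1.3. In the middle case this is 5.4 × 0.5 × 0.6/1.3 = 1.25 points, with type I error 14.1%. Adjusting for only one leaves 5.4 × d × 0.7r/1.3 = 5.4 × 0.5 × 0.21/1.3 = 0.44 points, or 35%. Adjusting for both leaves about 0. Simulation (8,000 runs) of the middle case gave type I errors of 14.7% (group only), 6.2% (one covariate) and 5.1% (both).

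**4. What the form of 5.3.3 leaves.** For a covariate that is binary by nature, such as sex, the stratum effects are free of imbalance in that covariate but not in the others. For a continuous covariate cut in two, imbalance persists inside each stratum. Under normality, the share of the bias left is the difference in truncated-normal means within the stratum, divided by d:

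- cut midway between the group means: 36% in each stratum;
- cut 0.5 SD away: 27% and 49%;
- cut 1 SD away: 20% and 63%.

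A continuous linear term removes this bias if the relation is linear and the covariate is well measured. At reliability 0.8, 20% stays: 0.06 to 0.30 points over the range in step 2.

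**5. Power of a jointly adjusted model.** With four covariates, SE = 5.4 × √(1 − R²change) × √[(1/n₁ + 1/n₂)/(1 − R²group)] and df = n₁ + n₂ − 6.

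| R²change | R²group | 56 v 20 | 50 v 18 |
|---|---|---|---|
| 0 | 0 | 80.1% | 75.6% |
| 0 | 0.10 | 75.8% | 71.1% |
| 0 | 0.20 | 70.8% | 66.0% |
| 0.10 | 0.10 | 80.1% | – |
| 0.25 | 0.10 | 86.7% | 82.8% |

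The four degrees of freedom alone cost almost nothing (80.14% to 80.08%). The 50 v 18 column illustrates losses from missing covariates.

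**6. Baseline ACE.** Suppose a 0.5 SD baseline difference, equal pre and post SDs, and pre/post correlation ρ of 0.6 to 0.8. If both groups follow one regression line, the change-score model is biased by 0.5 × 5.4 × √[(1 − ρ)/2] = 1.21 to 0.85 points (type I error 13.5% to 9.2%). If the groups instead change in parallel, the baseline-adjusted model is biased by the same amount. Neither model is safe by default.

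**The case against.** **The size is assumed.** Only 56, 20, 4, 5.4 and 5% come from the SAP. The low case is negligible, and the two-covariate case needs both imbalances to point the same way. This stands: the figures show a risk and do not show that the result will be biased.

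**The change score was a considered choice.** The reference list includes a paper on choosing between difference scores and covariance adjustment. This supports caution about adding baseline ACE to the main model. It does not answer the absence of adjustment for anything else.

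**Section 5.3.3 already adjusts.** It does, partly. Each model carries a covariate main effect, but the interaction makes the output stratum effects. There is no overall effect, the other covariates are left out, and the sub-scores are not covered.

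**Adjustment has a price.** With 20 controls, power falls to 75.8% or 70.8% if the covariates predict group but not change. Self-selection and other unmeasured factors remain. The choice of covariates is also a judgement, since the SAP does not rank its ten. These points stand, and they are good reasons to keep the list short and the crude estimate visible. They are not reasons to plan no adjusted estimate.

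**Conclusion.** The concern holds. That the SAP plans no jointly adjusted overall estimate is certain from its text. The consequence is conditional: over the assumed range for a single covariate, it runs from negligible to a bias of more than a third of the target difference. The crude analysis can be run and is transparent, but in a non-randomized comparison its p-value and interval cannot alone support calling the group term an intervention effect. This should be corrected before groups are compared.

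**What to change.** **Model.** In 5.3.1 prespecify, for the global score and each sub-score in Table 2, improvement on group, age, sex, years of education and cognitive reserve score, with age, education and reserve continuous. These four covariates are a proposal. Hypothesis 4 names other candidates (history of dementia, chronic disease, lifestyle, medication). Fix a short list beforehand.

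**Reporting.** Show the adjusted coefficient with its 95% CI beside the group-only estimate in Table 2, and state before analysis which is primary. The adjusted model is the better basis for reading the group term as an intervention effect. In 3.7, say that the 80% refers to the group-only model.

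**Sensitivity.** Add a model that also includes baseline ACE, or the matching baseline sub-score. State that it and the change-score model rest on different assumptions.

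**Effect sizes.** Define the non-standardized effect as the group coefficient of the model shown. Define the standardized effect as that coefficient divided by the pooled within-group SD of improvement, with a bootstrap CI resampled within group. The Table 2 footnote currently names a standard error as divisor, a separate fault to correct at the same time: 4/5.4 = 0.74 with the SD, 4/1.407 = 2.84 with the standard error.

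**Missing covariates.** Check them before improvement is compared between groups. If one exceeds the 20% limit in 5.4, drop it from the adjusted model for all outcomes and say so under Table 2. Refit the group-only model on the adjusted model's complete cases and report N per group for each model.

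**Cost.** SAP wording, extra table rows, a few lines of R and four degrees of freedom. The baseline data are already to be collected. Power may fall or rise as in step 5 of the working. Only measured, adequately modelled factors are addressed, and a baseline ACE difference is handled only in the sensitivity model.

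### The interaction tests for primary objective 4 use age, education and cognitive reserve only as two groups, giving up roughly 25% to 50% of the information if modulation is linear

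*SAP*

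**What the plan says.** SAP section 3.3 lists objective 4 among the primary objectives: "Determine if there are response phenotypes based on the distribution of individual baseline characteristics". Section 5.3.3 gives the method, one linear model per covariate: "The primary outcome will be modelled with the covariate of interest, the group variable, and their interaction". It then states the purpose of the interaction: "This interaction term will assess whether the intervention effect varies across covariate groups". The list of covariates and subgroups that follows defines the groups, among them "Age (<=65 years, >65 years", "Years of Education (<=12 years, >12 years" and "Cognitive reserve (low, high". The SAP states no threshold for low and high reserve, and it plans no model with these covariates on their original scale.

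Finer values are held for all three:

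- **Age and education.** Dummy Table 1 asks for mean and SD of both. Section 3.6 admits "Adults aged 21 years and above" with no upper limit.
- **Cognitive reserve.** Section 3.8 describes a scale: "A total of 24 items are distributed across four aspects". Sections 3.3 and 5.3.3 both call it a score.

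**The concern.** A two-group term assumes that the program effect is constant within each half and jumps at the cut. For age, this treats a participant of 21 and one of 65 as alike, and separates 65 from 66. If modulation is gradual, the cut discards information about it. The interaction tests are already limited by the 20 controls, so the loss falls on a primary objective with little power to spare. For cognitive reserve the answer also depends on a cut that the SAP does not fix.

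Subgroups are the natural display for a forest plot. That does not require the hypothesis test to be run on the same split.

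**Working it through.** **Inputs from the SAP.** Section 3.7 gives 56 intervention and 20 control subjects, a difference of 4 points and a maximum SD of 5.4. Section 5.5 gives a two-sided 5% level.

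**Assumptions, not in the SAP.** The covariate is normal or uniform with the same distribution in both groups. The modifying effect is linear, with illustrative slopes of 2, 3 and 4 ACE points per SD of the covariate. The residual SD is 5.4.

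**1. The plan's own figure.** SE = 5.4 × √(1/56 + 1/20) = 1.407, and 4/1.407 = 2.84. Power is 81.2% by the normal approximation and 80.1% by the noncentral t with 74 df. The stated power of at least 80% reproduces. It concerns the main group comparison; the SAP gives no figure for the interactions.

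**2. Information kept by a cut.** For a linear effect this is the squared correlation between the covariate and its indicator. With a fraction p on one side of the cut, it is φ(z_p)²/[p(1−p)] for a normal covariate and 3p(1−p) for a uniform one.

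| Split | Normal: kept | Normal: lost | Uniform: kept | Uniform: lost |
|---|---|---|---|---|
| 50/50 | 0.399²/0.25 = 0.637 | 36% | 0.75 | 25% |
| 30/70 | 0.576 | 42% | 0.63 | 37% |
| 20/80 | 0.280²/0.16 = 0.490 | 51% | 0.48 | 52% |

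For a normal covariate this equals using about 48 of 76 subjects at 50/50 (76 × 0.637) and 37 at 20/80 (76 × 0.490). A strongly bimodal covariate cut between its modes loses less, about 19%.

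**3. Interaction power, closed form.** For the continuous term, the SE of the difference in slope per SD is 1.407. For a median split the SE is 5.4 × √[4 × (1/56 + 1/20)] = 2.81, and the expected difference between halves is slope × 0.399/0.25 = 1.596 × slope. At slope 4 the ratio of effect to SE is 4/1.407 = 2.84 continuous, against 6.38/2.81 = 2.27 split. With 72 df, power is 80% against 61% at slope 4, 56% against 39% at slope 3, and 29% against 20% at slope 2.

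**4. Interaction power, simulated.** The closed form ignores chance variation in the covariate's spread among only 20 controls. Simulating the linear models (20,000 runs per setting, normal covariate) gives slightly lower values:

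| Slope, points per SD | Continuous | Median split | 25/75 split |
|---|---|---|---|
| 4 | about 75% | 53% | 44% |
| 3 | about 52% | 35% | 28% |
| 2 | about 27% | 19% | 16% |

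**5. The opposite case.** If the effect truly steps by 8 points at the cut, the split has about 78% power and the linear term about 53% at a median cut; at 25/75 the figures are about 64% and 36%.

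**6. What the split can detect.** The two-group difference in effect detectable with 80% power is about 7.9 points at 50/50 and 9.9 at 20/80, where one stratum has about 4 controls.

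**The case against.** The case for leaving the plan as it is has four parts.

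- **The loss depends on unknown distributions.** This stands. A reader might infer that at least a third of the information is always lost, but that is the minimum for a normal covariate only. Age with no upper limit and education in whole years need not be normal, and a uniform covariate cut at its median loses 25%. Equally, nothing places 65 or 12 years near the sample median, and a cut well away from it generally costs more.
- **The illustrative slopes are large.** This stands too. Four points per SD means that the program effect changes by 8 points between −1 and +1 SD, twice the design difference. If the modulation acts in the intervention arm, that arm's SD becomes √(5.4² + 4²) = 6.7, above the stated maximum of 5.4. The row for 2 points per SD is the more sober guide. A reader might infer that a continuous term would make objective 4 well powered. The figures do not support that: the 20 controls remain the limit.
- **Response phenotypes suggest groups, and a true step favours the split.** The second half is correct, as step 5 shows. But the SAP gives no reason to expect steps at these particular cuts.
- **The cuts are prespecified.** This is true of age and education, so it would be wrong to infer that those results hang on a cut chosen from the data. Only the reserve cut is open in the SAP.

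**Conclusion.** The point holds as a matter of efficiency. For age, years of education and cognitive reserve, section 5.3.3 tests a primary objective on two-group versions of covariates collected in finer form. If modulation is linear, the loss is about 36% (normal) or 25% (uniform) at a median cut, and 51% or 52% at 20/80. For a normal covariate at a median cut, that is about 8 to 22 percentage points of interaction power over slopes of 2 to 4 points per SD. These sizes rest on the assumed distributions, linearity, illustrative slopes and a residual SD of 5.4. The tests stay weak for modest modulation whichever form is used. The main comparison of ACE improvement in section 5.3.1 is not affected.

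**What to change.** In section 5.3.3, state that the interaction test for age, years of education and cognitive reserve score uses the continuous covariate, centred, and reports the difference in slope between groups with its 95% CI. Keep the listed categories for the forest plot and as a supportive analysis, and state the low/high threshold for reserve, which that display still needs.

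The cost is about one sentence of text, with no new data and no change to the figure. The price is an assumed linear trend, which a plot can check only roughly with 20 controls; the supportive two-group analysis gives some cover if the effect is step-like. Baseline ACE is also cut in two, but it is part of the change score and its scale is capped at 100, so its form needs separate justification and is not included here.
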